10.4 Appendix 4: Protocol Amendments

The investigator or subinvestigator will not make any changes to this protocol without the sponsor's prior written consent and subsequent approval by the IRB. Any permanent change to the protocol, whether an overall change or a change for specific trial site(s), must be handled as a protocol amendment. Any amendment will be written by the sponsor. Each amendment will be submitted to the IRB, as required by local regulations. Except for "administrative" or "nonsubstantial" amendments, investigators or subinvestigator will wait for IRB approval of the amended protocol before implementing the change(s). Administrative amendments are defined as having no effect on the safety of subjects, conduct or management of the trial, trial design, or the quality or safety of IMPs used in the trial. A protocol change intended to eliminate an apparent immediate hazard to subjects should be implemented immediately, followed by IRB notification within local applicable timelines. If required, the sponsor will submit protocol amendments to the applicable regulatory agencies within local applicable timelines.

When the IRB, investigators, and/or the sponsor conclude that the protocol amendment substantially alters the trial design and/or increases the potential risk to the subject, the currently approved written ICF will require similar modification. In such cases, after approval of the new ICF by the IRB, repeat written informed consent will be obtained from subjects enrolled in the trial before expecting continued participation and before the amendment-specified changes in the trial are implemented.

Black box for the final answer.

[REDACTED]

Black box for the final answer

Page 10

For more information, contact the Office of the Vice President for Research and Economic Development at [contact] or [contact].

[figure not shown]
[REDACTED]

ANSWER

For more information, contact the Office of the Vice President for Research and Economic Development at [contact] or [contact].

For more information, contact the Office of the Vice President for Research and Economic Development at [contact] or [contact].

[REDACTED]

ADDITIONAL RISK TO THE SUBJECT:

There is no additional risk to the subjects.

11 References

- ¹ Japan Atherosclerosis Society. Guidelines for Prevention of Atherosclerotic Cardiovascular Diseases 2017. 2017.

List of Appendices

Appendix 1	Criteria for Identifying Vital Signs and Weight of Potential Clinical Relevance	23
Appendix 2	Criteria for Identifying Laboratory Values of Potential Clinical Relevance	24
Appendix 3	Criteria for Identifying ECG Measurements of Potential Clinical Relevance	25
Appendix 4	Preferred Terms for Statins and Ezetimibe	26
<hr/>		
Appendix 6	List of Figures and Tables	31
Appendix 7	List of Subject Data Listings	39

List of Abbreviations and Definition of Terms

Abbreviation	Definition
ALP	Alkaline phosphatase
ALT	Alanine aminotransferase
apo B	Apolipoprotein B
AST	Aspartate aminotransferase
BMI	Body mass index
CRF	Case report form
FAS	Full analysis set
HbA1c	Glycosylated hemoglobin
HDL-C	High-density lipoprotein cholesterol
hsCRP	High-sensitivity C-reactive protein
ICH	International Council for Harmonisation of Technical Requirements for Pharmaceuticals for Human Use
LDL	Low-density lipoprotein
LDL-C	Low-density lipoprotein cholesterol
MedDRA	Medical Dictionary for Regulatory Activities
MMRM	Mixed-model repeated measures
non-HDL-C	Non-high-density lipoprotein cholesterol
PPAR	Peroxisome proliferator-activated receptor
PT	Preferred term
QTc	Corrected QT interval
QTcF	QT interval corrected for heart rate using Fridericia's formula
SAS	Statistical Analysis System
SOC	System organ class
TC	Total cholesterol
TEAE	Treatment-emergent adverse event
TG	Triglyceride
WHODD	World Health Organization Drug Dictionary

1 Introduction

This statistical analysis plan (SAP) documents the detailed methods for the statistical analysis planned in Trial 346-102-00001.

2 Trial Objectives

Primary:

- To assess the low-density lipoprotein cholesterol (LDL-C)-lowering efficacy of ETC-1002 at 60 mg, 120 mg, and 180 mg versus placebo when administered for 12 weeks in combination with ongoing stable statin therapy and/or other lipid-modifying therapy in patients with hypercholesterolemia who have inadequate control of LDL-C
- To characterize the dose-response of ETC-1002 and investigate the appropriate dosage for a phase 3 trial

Secondary:

- To assess the effect of ETC-1002 on high-density lipoprotein cholesterol (HDL-C), non-high-density lipoprotein cholesterol (non-HDL-C), total cholesterol (TC), triglyceride (TG), apolipoprotein B (apo B), high-sensitivity C-reactive protein (hsCRP), and glycosylated hemoglobin (HbA1c)
- To assess the proportion of subjects achieving the lipid management goal of LDL-C by treatment with ETC-1002
- To assess the pharmacokinetic plasma trough and near-peak concentrations of ETC-1002 and its active metabolite (ESP15228)
- To characterize the safety and tolerability of ETC-1002 in patients with hypercholesterolemia when administered in combination with ongoing stable statin therapy and/or other lipid-modifying therapy

3 Trial Design

[figure not shown]
3.1 Type/Design of Trial

This is a placebo-controlled, randomized, multicenter, double-blind, parallel-group trial to assess the efficacy and safety of ETC-1002 in patients with hypercholesterolemia who are being treated with hypercholesterolemia drugs but have inadequate control and cannot achieve the lipid management goal. The trial population will include patients with statin tolerance who do not sufficiently respond to statins and cannot achieve the lipid management goal despite being treated with statins, and patients with statin intolerance who have experienced safety problems at the time of starting or increasing the dose of statins, that were successfully resolved after stopping or reducing the dose of statins, and

cannot achieve the lipid management goal in spite of taking statins at (or below) the lowest approved daily dose and/or hypercholesterolemia drugs other than statins.

A schematic of the trial design is presented in [Figure 3.1-1](#). This trial consists of the screening period, [REDACTED] the treatment period, and the follow-up period.

Subjects determined to be eligible in the screening period will [REDACTED]
[REDACTED] continue the treatment without changing the type and the dose and regimen
of hypercholesterolemia drugs that have been taken from before informed consent [REDACTED]
[REDACTED]
[REDACTED]
[REDACTED] Subjects [REDACTED]
[REDACTED] who do not
fall under the exclusion criteria as judged by the investigator or subinvestigator will be
assigned either to the ETC-1002 60-mg/day, 120-mg/day, 180-mg/day, or placebo group
and proceed to the treatment period. Statin response (statin tolerance/statin intolerance) is
set as a randomization stratification factor so that subjects with statin intolerance will be
equally allocated to each treatment group.

3.2 Trial Treatments

In the treatment period, subjects will receive either of ETC-1002 60 mg/day, 120 mg/day, 180 mg/day, or placebo for 12 weeks in addition to continued hypercholesterolemia drugs that have been taken from before informed consent. The medications to be taken in the [REDACTED] treatment period are detailed below.

Black box for the first part of the question

Black box for the final answer

© 2013 Pearson Education, Inc.

11. **What is the primary purpose of the *Journal of Clinical Endocrinology and Metabolism*?**

Page 10

© 2013 Pearson Education, Inc.

© 2013 Pearson Education, Inc.

Page 1 of 1

100

For more information, contact the Office of the Vice President for Research and Economic Development at [contact] or [contact].

1000

10

[REDACTED]

3.2.2 Treatment period

1) Medications

- Mandatory concomitant medications:
Hypercholesterolemia drugs (statins and/or drugs other than statins) that have been taken from before informed consent
- IMP:
 - ETC-1002 60-mg tablets
 - Placebo tablets

2) Dose and regimen

- Mandatory concomitant medications:
Hypercholesterolemia drugs [REDACTED] will be continued without changing the type and the dose and regimen during the treatment period.
- IMP:

- 180-mg/day group: Three ETC-1002 60-mg tablets will be administered orally once daily.
- 120-mg/day group: Two ETC-1002 60-mg tablets and one placebo tablet will be administered orally once daily.
- 60-mg/day group: One ETC-1002 60-mg tablet and two placebo tablets will be administered orally once daily.
- Placebo group: Three placebo tablets will be administered orally once daily.

3) Treatment duration

12 weeks

3.3 Trial Population

This trial will be conducted in Japanese patients with hypercholesterolemia who are aged 20 years or older and younger than 75 years at the time of informed consent and who are being treated with hypercholesterolemia drugs but have inadequate control and cannot achieve the lipid management goal. Subjects [REDACTED]
[REDACTED]
[REDACTED]

[REDACTED] those confirmed by the investigator or subinvestigator not to fall under the exclusion criteria will be randomized. The target number of randomized subjects is 176 in total (44 in the ETC-1002 60-mg/day group, 44 in the 120-mg/day group, 44 in the 180-mg/day group, and 44 in the placebo group). In addition to patients with statin tolerance, patients with statin intolerance will be enrolled at $\geq 20\%$ of the total. Statin response (statin tolerance/intolerance) is set as a randomization stratification factor so that subjects with statin intolerance will be equally allocated to each treatment group.

3.4 Trial Visit Window

Data observed at CRF Visit will be used at each analysis visit (but data at discontinuation will not be used in analysis). Data from unscheduled visits will not be used. Efficacy analysis will be performed using the data obtained up until 2 days after final IMP administration. In assessment of efficacy endpoints, baseline for fasting lipid parameters is defined as the mean of the values for Day 1 (Visit T1) and Week -1 (Visit S3). If only one value is obtained, that value will be used as baseline. For efficacy endpoints other than fasting lipid parameters, baseline is defined as the value for Day 1 (Visit T1). For safety endpoints, baseline is defined as the last data obtained prior to initial IMP administration in the treatment period.

4 Sample Size

Differences in the percent change in LDL-C from baseline to Week 12 in the ETC-1002 group versus the placebo group in non-Japanese phase 3 trials were -18.1% and -17.42% in trials in statin tolerant subjects and -21.41% and -28.45% in trials in statin intolerant subjects. Based on the results, the difference between the ETC-1002 group and the placebo group in the subjects with statin tolerance was assumed to be 17% , and the difference between the ETC-1002 group and the placebo group in the subjects with statin intolerance was assumed to be 25% . For the present trial it was assumed that the percentage of statin intolerant subjects enrolled would be 20% and that the difference in the endpoint between the ETC-1002 group and the placebo group would be 19% in the overall trial population. Based on the results of the phase 3 trials, assuming a difference of 19% with standard deviation of 25% between the ETC-1002 groups and the placebo group in the percent change in LDL-C from baseline to Week 12, 38 subjects per group are required to achieve a power of 90% or higher in a two-tailed test with a 5% significance level. Assuming a withdrawal rate of 12.5% , the target number of subjects to be randomized was set at 44 per group.

5 Statistical Analysis Datasets

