9.4.2.3 Vital Signs Data

For vital signs (blood pressure, pulse rate, and body temperature), descriptive statistics of the actual value and change from baseline will be calculated at each time point.

The number and percentage of subjects meeting Criteria for Identifying Vital Signs of Potential Clinical Relevance will be calculated (the criteria will be specified in the SAP).

9.4.2.4 *Electrocardiogram Data*

For ECG parameters (heart rate, PR interval, RR interval, QRS interval, QT interval, and QTcF), descriptive statistics of the actual value and change from baseline will be calculated at each time point.

The number and percentage of subjects with a QTcF of >450 msec, >480 msec, or >500 msec at any postdose time point will be calculated. In addition, the number and percentage of subjects who have a change in QTcF from baseline of >30 msec or >60 msec at any postdose time point will be calculated. The number and percentage of subjects meeting these criteria at baseline or each postdose time point will also be calculated.

For assessment of normality/abnormality, shift tables at baseline and each time point will be prepared.

The number and percentage of subjects meeting Criteria for Identifying ECG Measurements of Potential Clinical Relevance will be calculated (the criteria will be specified in the SAP).

9.4.2.5 *Other Safety Data*

9.4.2.5.1 *Body weight*

Descriptive statistics of the actual value and change from baseline will be calculated at each time point.

9.4.3 *Other Analyses*

9.4.3.1 *Analysis of Demographic and Baseline Characteristics*

Frequency distributions or descriptive statistics of each item for demographic and other baseline characteristics will be calculated by treatment group (by dose and overall for ETC-1002) in each analysis set.

9.4.3.2 *Pharmacokinetic Analysis*

In the PK analysis set, descriptive statistics (number of subjects, mean, standard deviation, coefficient of variation, minimum, median, and maximum) will be calculated for the plasma concentrations of ETC-1002 and its active metabolite ESP15228 at each dose, visit, and post-dose time point. Population pharmacokinetic analysis of ETC-1002 will be performed separately.

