5.4 Handling of Missing Data

In the primary analysis of the primary endpoint, when the LDL-C value at Week 12 is missing, the missing value will be imputed using the last value observed from after initial IMP administration up until 2 days after final IMP administration (last observation carried forward: LOCF).

In analysis of the percent change from baseline to Week 12 for secondary endpoints and of the proportion of subjects achieving the lipid management goals of LDL-C, missing values will be handled in the same manner as above. Missing values will not be imputed for sensitivity analysis and pharmacokinetic analysis.

Fasting lipid parameters will be handled as shown in the table below.

Condition	Fasting Lipid Parameters
Parameter to be used in analysis, irrespective of fasting condition	LDL-C (direct measurement)
Parameters to be used in analysis only when obtained under a fasting condition	LDL-C (Friedewald formula), HDL-C, non-HDL-C, TC, TG

6 Primary and Secondary Outcome Variables

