8.3 Subgroup Analyses

Subgroup analyses will be performed by the following items for the percent change in LDL-C from baseline to Week 12, the primary endpoint. Using the same analysis of covariance as for the primary analysis, the least squares mean for each treatment group and the differences in the mean of the least squares between each ETC-1002 group and the placebo group, together with the two-sided 95% confidence intervals, will be calculated for each subgroup. In the analysis for the statin response subgroup, the randomization stratification factor (statin response) will not be included in the model.

- Statin response (statin tolerance, statin intolerance)
- Sex (male, female)

- Familial hypercholesterolemia (yes, no)
- Diabetes mellitus (yes, no)
- Age (<65 years, \geq 65 years)
- Statin use (yes, no)

9 Safety Analyses

Tabulation by treatment group (by dose and overall for ETC-1002) will be performed in the safety analysis set. Baseline is defined as the last data before the start of IMP administration in the treatment period. The same tabulation will be performed by the randomization stratification factor (statin response). In addition to analysis for the specified visit, an additional analysis will be conducted at Week 12 with missing data being imputed based on the LOCF principle (Week 12 [LOCF]). The procedure for imputation will be the same as that for efficacy endpoints.

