9.3 Clinical Laboratory Data

Among parameters of the urinalysis in the laboratory tests, the qualitative urinalysis includes parameters other than pH and specific gravity.

For parameters other than qualitative urinalysis, descriptive statistics of the actual value and change from baseline will be calculated at each visit. For qualitative urinalysis parameters, shift tables at each visit from baseline will be prepared. For parameters other than qualitative urinalysis, measured values will be categorized using the reference range to “below the lower limit of reference range”, “within the reference range” and “above the upper limit of reference range”, and shift tables at each visit from baseline will be prepared.

The number and percentage of subjects meeting the criteria for identifying laboratory values of potential clinical relevance ([Appendix 2: Criteria for Identifying Laboratory Values of Potential Clinical Relevance](#)) will be calculated.

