9.6 Electrocardiogram Data

For ECG parameters (heart rate, PR interval, RR interval, QRS interval, QT interval, and QTcF), descriptive statistics of the actual value and change from baseline will be calculated at each visit.

The number and percentage of subjects with a QTcF of >450 msec, >480 msec, or >500 msec at any postdose visit will be calculated. In addition, the number and percentage of subjects who have a change in QTcF from baseline of >30 msec or

>60 msec at any postdose visit will be calculated. The number and percentage of subjects meeting these criteria at each postdose visit will also be calculated.

For assessment of normality/abnormality, shift tables at each visit from baseline will be prepared.

The number and percentage of subjects meeting the criteria for identifying ECG measurements of potential clinical relevance ([Appendix 3: Criteria for Identifying ECG Measurements of Potential Clinical Relevance](#)) will be calculated.

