9.7 Other Safety Data

9.7.1 Body weight

Descriptive statistics of the actual value and change from baseline will be calculated at each visit.

The number and percentage of subjects meeting the criteria for identifying body weight of potential clinical relevance ([Appendix 1: Criteria for Identifying Vital Signs and Weight of Potential Clinical Relevance](#)) will be calculated.

10 Pharmacokinetic Analyses

For the PK analysis set, descriptive statistics (number of subjects, number of subjects actually analyzed, mean, standard deviation, coefficient of variation, minimum, median, and maximum) will be calculated for the plasma concentrations of ETC-1002 and its active metabolite ESP15228 at each dose, visit, and postdose time point (before or at 2 to 4 hours after administration at each visit). In the calculation of descriptive statistics, plasma drug concentrations below the lower limit of quantitation will be regarded as “0” (zero).

Timecourse plots of the plasma drug concentrations of ETC-1002 and its active metabolite ESP15228 before administration at each visit will be prepared (horizontal axis: visit, longitudinal axis: plasma drug concentration). The mean \pm standard deviation of plasma drug concentrations before administration at each visit calculated by dose and by visit will be plotted. Similarly, the individual timecourses for all subjects will be plotted by dose.

11 Pharmacodynamic Analyses

No pharmacodynamic analysis is planned.

12 Pharmacogenomic Analyses

No pharmacogenomic analysis is planned.

13 Interim Analysis

No interim analysis is planned.

14 Changes in the Planned Analyses

Regarding the definition of the pharmacokinetic analysis set in [Section 5.3](#), since measurement results of plasma drug concentration will not be available at the time of unblinding, an equivalent analysis set is defined based on available records on the time of blood sampling.

Regarding the following calculations for QTcF in ECG in [Section 9.6](#), calculations at baseline that were planned in the protocol will not be performed.

- The number and percentage of subjects with a QTcF of >450 msec, >480 msec, or >500 msec at any postdose time point will be calculated.
- The number and percentage of subjects who have a change in QTcF from baseline of >30 msec or >60 msec at any postdose time point will be calculated.

15 References

Not applicable.

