Appendix 1 Criteria for Identifying Vital Signs and Weight of Potential Clinical Relevance

Variable	Criterion Value ^a	Change Relative to Baseline ^a
Pulse Rate	>120 bpm <50 bpm	≥15 bpm increase ≥15 bpm decrease
Systolic Blood Pressure	>160 mmHg <90 mmHg	≥20 mmHg increase ≥20 mmHg decrease
Diastolic Blood Pressure	>100 mmHg <50 mmHg	≥15 mmHg increase ≥15 mmHg decrease
Weight	N/A	≥7% increase ≥7% decrease

^aIn order to be identified as potentially clinically relevant, an on-treatment value must meet the “Criterion Value” and also represent a change from the subject’s baseline value of at least the magnitude shown in the “Change Relative to Baseline” column.

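### SAP 3.4 excludes discontinuation and unscheduled-visit data without limiting the rule to efficacy or by-visit summaries, so subject-level safety threshold counts can miss some crossings

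*SAP*

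**What the plan says.** SAP 3.4 assigns the data of each CRF visit to an analysis visit. A parenthesis and the sentence after it then remove two kinds of record: "but data at discontinuation will not be used in analysis). Data from unscheduled visits will not be used". The following sentence, on the 2-day cut-off after the final dose, is expressly about efficacy. The section ends by defining the safety baseline.

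The safety sections call for subject-level counts. SAP 9.3 asks for "The number and percentage of subjects meeting the criteria for identifying laboratory values of potential clinical relevance" (Appendix 2). SAP 9.4, 9.6 and 9.7.1 ask for the same for vital signs, ECG and body weight (Appendices 1 and 3). For QTcF, SAP 9.6 has the number of subjects above each limit in "msec at any postdose visit will be calculated"; Protocol 9.4.2.4 has "msec at any postdose time point will be calculated". The footnote shared by Appendices 1 and 3 says that "to be identified as potentially clinically relevant, an on-treatment value must meet the" criterion; Appendix 2 has no such footnote.

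SAP 9 adds a Week 12 (LOCF) safety analysis: "The procedure for imputation will be the same as that for efficacy endpoints". That procedure, in SAP 5.4, carries forward the "last value observed from after initial IMP administration up until 2 days after final IMP administration".

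SAP 14 records one change to the QTcF counts: "calculations at baseline that were planned in the protocol will not be performed". It records no restriction of safety counts to scheduled visits.

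**The concern.** A count of subjects who ever crossed a safety limit normally draws on every qualifying post-dose value, because the crossing may occur between planned visits or at the visit where the subject leaves. A rule that suits by-visit means and shift tables does not suit such a count. If SAP 3.4 is applied to all analyses, a subject whose only abnormal value was taken at withdrawal, or at an extra laboratory test, stays in the safety analysis set but is not counted as having crossed.

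The tables affected compare safety by dose in a dose-finding trial. They are descriptive and no test hangs on them, but two programmers could read SAP 3.4 differently and produce different counts.

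**Working it through.** **1. Scope of the rule.** Three features of SAP 3.4 bear on it.
- Neither exclusion mentions efficacy. The next sentence does, so a limit is stated there and not here.
- The section also sets the safety baseline, so it is not confined to efficacy data.
- The discontinuation exclusion sits in a parenthesis within the visit-assignment sentence. The unscheduled-visit exclusion is a free-standing sentence without that lead-in.

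**2. Does a later section restore the values?** SAP 9.3, 9.4, 9.6 and 9.7.1 and Appendices 1 to 3 say which limits apply. They do not say that withdrawal or unscheduled records enter. SAP 9.6 asks separately for QTcF counts over any post-dose visit and at each post-dose visit, so a by-visit assignment rule alone does not settle which records feed the first. Protocol 9.4.2.2 to 9.4.2.4 attaches no scheduled-visit limit to these counts.

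**3. Do such records exist?**
- Withdrawal examination: Protocol 1.3.7 and 7.3.2 provide for it, as far as feasible, with results recorded in the eCRF. Its content is in Table 1.3-1, which is not shown. Appendices 1 to 3 and QTcF are affected only so far as it includes the relevant assessment, and Appendices 1 and 3 only if the value is on treatment.
- Extra tests: Protocol 8.8.1 lets the investigator repeat a laboratory test or request more. This bears on Appendix 2 only, and only if the sample is recorded as an unscheduled visit. A repeat that confirms a scheduled value already counted loses nothing.

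**4. How many subjects might have a withdrawal value?** Inputs are from SAP 4 and 3.3: difference 19, SD 25, two-sided 5%, power 90%, 12.5% withdrawal, 44 per arm, 176 in total.
- Plan's figure, normal approximation: n = 2 × (1.960 + 1.282)² × (25/19)² = 36.4, so 37. The two-sample t-test gives 37.4, so 38, with power 90.5% at 38. The stated 38 is reproduced.
- Inflation: 38 / (1 − 0.125) = 43.4, so 44. Reproduced.
- Expected withdrawals: 0.125 × 44 = 5.5 per arm; 0.125 × 176 = 22 in all. The gap between randomized and required is 44 − 38 = 6 per arm.

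**5. Weight of one missed subject.** SAP 9.3 to 9.7 does not state the denominator. One subject is 1/44 = 2.3 percentage points, or 1/38 = 2.6. Over the three active arms combined it is 1/132 = 0.8. No share of crossings is assumed, because the documents give no basis for one.

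**The case against.** The strongest reply is that SAP 3.4 is headed as a visit-window section and that the discontinuation exclusion belongs to a sentence on assigning data to analysis visits. On that reading it says only that withdrawal data are not placed at a nominal visit. This is reasonable for the parenthesis. It fits the unscheduled-visit sentence less well, and nothing elsewhere in the SAP confirms it.

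The second reply is that other outputs catch what matters. Under Protocol 8.8.1, a laboratory value judged clinically significant, leading to discontinuation or meeting a seriousness criterion is an adverse event, and SAP 9.2 tabulates these by arm. Combined transaminase and bilirubin elevation is reported immediately and as an adverse event (Protocol 8.8.6). SAP Appendices 6 and 7 plan listings of abnormal laboratory findings, laboratory values, vital signs and ECG. This stands and limits the harm. It does not replace threshold counts by arm: an isolated crossing in CK, creatinine, uric acid or ALT need not become an adverse event.

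Four stronger inferences are tempting, and the documents do not support them.
- A reader might take the QTcF change from time point to visit as an undeclared restriction. The SAP makes the same substitution for laboratory data, vital signs, other ECG summaries, body weight and efficacy descriptives, and a withdrawal or unscheduled visit is still a visit.
- A reader might see a contradiction between SAP 3.4 and 5.4 over LOCF. If 3.4 is visit assignment, a withdrawal value can still be carried forward; if it is a general exclusion, the last usable value is. Each reading is coherent, so this is an ambiguity.
- A reader might extend the repeat-test route to vital signs, weight or ECG. The protocol documents it for laboratory tests only.
- A reader might ask whether Week 16 values inflate the Appendix 2 and QTcF counts. That depends on Table 1.3-1, so no finding can be made.

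**Conclusion.** The point holds, as a minor one. SAP 3.4 as written excludes discontinuation and unscheduled-visit data from analysis generally, the safety sections do not restore them, and SAP 14 does not declare a restriction. The subject-level counts can therefore be too low by any crossing seen only in those records, within the limits in steps 2 and 3 of the working.

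The size of the loss cannot be estimated. The 5.5 per arm is a planning allowance, neither a bound nor a count of missed crossings. Some subjects will withdraw for reasons unrelated to safety, some will have no withdrawal examination, and scheduled values before withdrawal still count. The loss could fall unequally across doses if withdrawals do, but the documents give no ground to expect that. The conclusion assumes that the withdrawal examination includes at least some of the safety assessments concerned.

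**What to change.** - In SAP 3.4, limit the exclusion to by-visit summaries and shift tables.
- For the Appendix 1 to 3 counts and the any-post-dose QTcF counts, use all post-dose values, including withdrawal and unscheduled ones, within one stated analysis window after the last dose. State the denominator.
- Optionally show scheduled-visit-only counts beside them, because subjects tested more often have more chances to cross a limit.
- State whether a withdrawal value within 2 days of the last dose enters Week 12 (LOCF) under SAP 5.4 and 9.
- If restricting safety counts to scheduled visits is intended, declare it in SAP 14.

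The cost is SAP wording and one data-selection flag. No new assessments are needed.
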